### **17.3. Treatment of Missing and Spurious Data**

Spurious data, which were not clarified by the query process before CDMS closure, are indicated. If appropriate, descriptive and inferential analyses are performed both with /without such data.

#### **17.1. Exclusion of Particular Information**

No data from the previous defined analysis set are excluded from the analysis except those defined in chapter 5.5, if applicable.

#### **17.2. Descriptive Analyses**

If applicable, mean and median survival times are presented by using the Kaplan-Meier estimates. Kaplan-Meier survival figures are presented for illustration.

Other descriptive data will be presented via tables as specified in chapter 5.1.

#### **17.3. Hypotheses & Statistical Tests**

Differences of the survival curves BioMonitor versus control group are tested for statistical inference with the log-rank test.

The hazard ratio for the BioMonitor versus control group including 95%CI is calculated with the Cox regression model. In case of doubt about the validity of the Cox model, the assumption of proportional hazards is checked graphically by log-minus-log survival versus log-time plots.

## 18. Other sec. EP: Time to 1st hosp. resulting from stroke

### 18.1. Analysis set

This endpoint is analyzed exclusively for the final statistical analysis report based on the ITT analysis set.

### 18.2. Variables

#### *CIP Chapter 8.3.3.6 Time to first hospitalization resulting from stroke*

*Assessment of the time from randomization to the first hospitalization resulting from stroke or death resulting from stroke. A specified endpoint definition will be given by the members of the EAEC and documented in the charter agreement.*

Data file: Identifier patient_ display_id_full	Notes	Variable name	Variable label	Variable level	Nominal values
data_SAR	descr.	any_stroke_ITT_SAR 	Any hospitalization resulting from stroke or death resulting from stroke after effective randomization ITT	nominal	Yes / No
data_SAR	No report	date_1stroke_ITT_SAR 	Date of 1st hospitalization resulting from stroke or death resulting from stroke after effective randomization ITT	date	n.a.
data_SAR	descr.	days_effrand_to_1stroke_ITT_SAR 	Days from effective randomization to the 1st hospitalization resulting from stroke or death resulting from stroke or termination ITT	scale	n.a.

### **18.3. Treatment of Missing and Spurious Data**

Spurious data, which were not clarified by the query process before CDMS closure, are indicated. If appropriate, descriptive and inferential analyses are performed both with /without such data.

#### **18.1. Exclusion of Particular Information**

No data from the previous defined analysis set are excluded from the analysis except those defined in chapter 5.5, if applicable.

#### **18.2. Descriptive Analyses**

If applicable, mean and median survival times are presented by using the Kaplan-Meier estimates. Kaplan-Meier survival figures are presented for illustration.

Other descriptive data will be presented via tables as specified in chapter 5.1.

#### **18.3. Hypotheses & Statistical Tests**

Differences of the survival curves BioMonitor versus control group are tested for statistical inference with the log-rank test.

The hazard ratio for the BioMonitor versus control group including 95%CI is calculated with the Cox regression model. In case of doubt about the validity of the Cox model, the assumption of proportional hazards is checked graphically by log-minus-log survival versus log-time plots.

## 19. Other sec. EP: Time to 1st hosp. resulting from major bleeding

### 19.1. Analysis set

This endpoint is analyzed exclusively for the final statistical analysis report based on the ITT analysis set.

### 19.2. Variables

#### *CIP Chapter 8.3.3.7 Time to first hospitalization resulting from major bleeding*

*Assessment of the time from randomization to the first hospitalization resulting from major bleeding or death resulting from major bleeding. A specified endpoint definition will be given by the members of the EAEC and documented in the charter agreement.*

Data file: Identifier patient_ display_id_full	Notes	Variable name	Variable label	Variable level	Nominal values
data_SAR	descr.	any_bleed_ITT_SAR 	Any hospitalization resulting from major bleeding or death resulting from major bleeding after effective randomization ITT	nominal	Yes / No
data_SAR	No report	date_1bleed_ITT_SAR 	Date of 1st hospitalization resulting from major bleeding or death resulting from major bleeding after effective randomization ITT	date	n.a.
data_SAR	descr.	days_effrand_to_1bleed_ITT_SAR 	Days from effective randomization to 1st hospitalization resulting from major bleeding or death resulting from major bleeding or termination ITT	scale	n.a.

### **19.3. Treatment of Missing and Spurious Data**

Spurious data, which were not clarified by the query process before CDMS closure, are indicated. If appropriate, descriptive and inferential analyses are performed both with /without such data.

#### **19.1. Exclusion of Particular Information**

No data from the previous defined analysis set are excluded from the analysis except those defined in chapter 5.5, if applicable.

#### **19.2. Descriptive Analyses**

If applicable, mean and median survival times are presented by using the Kaplan-Meier estimates. Kaplan-Meier survival figures are presented for illustration.

Other descriptive data will be presented via tables as specified in chapter 5.1.

#### **19.3. Hypotheses & Statistical Tests**

Differences of the survival curves BioMonitor versus control group are tested for statistical inference with the log-rank test.

The hazard ratio for the BioMonitor versus control group including 95%CI is calculated with the Cox regression model. In case of doubt about the validity of the Cox model, the assumption of proportional hazards is checked graphically by log-minus-log survival versus log-time plots.

## 20. Other sec. EP: Time to 1st hosp. resulting from systemic embolism

### 20.1. Analysis set

This endpoint is analyzed exclusively for the final statistical analysis report based on the ITT analysis set.

### 20.2. Variables

#### *CIP Chapter 8.3.3.8 Time to first hospitalization resulting from systemic embolism*

*Assessment of the time from randomization to the first hospitalization resulting from systemic embolism or death resulting from systemic embolism. A specified endpoint definition will be given by the members of the EAEC and documented in the charter agreement.*

Data file: Identifier patient_ display_id_full	Notes	Variable name	Variable label	Variable level	Nominal values
data_SAR	descr.	any_emb_ITT_SAR 	Any hospitalization resulting from systemic embolism or death resulting from systemic embolism. after effective randomization ITT	nominal	Yes / No
data_SAR	No report	date_1emb_ITT_SAR 	Date of 1st hospitalization resulting from systemic embolism or death resulting from systemic embolism. after effective randomization ITT	date	n.a.
data_SAR	descr.	days_effrand_to_1emb_ITT_SAR 	Days from effective randomization to 1st hospitalization resulting from systemic embolism or death resulting from systemic embolism or termination ITT	scale	n.a.

### **20.3. Treatment of Missing and Spurious Data**

Spurious data, which were not clarified by the query process before CDMS closure, are indicated. If appropriate, descriptive and inferential analyses are performed both with /without such data.

#### **20.1. Exclusion of Particular Information**

No data from the previous defined analysis set are excluded from the analysis except those defined in chapter 5.5, if applicable.

#### **20.2. Descriptive Analyses**

If applicable, mean and median survival times are presented by using the Kaplan-Meier estimates. Kaplan-Meier survival figures are presented for illustration.

Other descriptive data will be presented via tables as specified in chapter 5.1.

#### **20.3. Hypotheses & Statistical Tests**

Differences of the survival curves BioMonitor versus control group are tested for statistical inference with the log-rank test.

The hazard ratio for the BioMonitor versus control group including 95%CI is calculated with the Cox regression model. In case of doubt about the validity of the Cox model, the assumption of proportional hazards is checked graphically by log-minus-log survival versus log-time plots.

## 21. Other sec. EP: Time to 1st arrhythmia

### 21.1. Analysis set

This endpoint is analyzed exclusively for the final statistical analysis report based on the ITT analysis set.

### 21.2. Variables

#### *CIP Chapter 8.3.3.9. Time to first arrhythmia*

*Assessment of the time from randomization to first arrhythmia.*

Data file: Identifier record_ID	Notes	Variable name	Variable label	Variable level	Nominal values
adverse_events	No report	arr_yn	NEW: Arrhythmia documented	nominal	Yes / No
advers_events	No report	arr_date	NEW: Earliest documentation of the arrhythmia	date	n.a.
adverse_events	No report	end_date	End date of AE (if applicable: Date of death)	date	n.a.

Data file: Identifier patient_display_id_full	Notes	Variable name	Variable label	Variable level	Nominal values
data_SAR	No report	any_arrhythmia_ITT_SAR 	Any arrhythmia after effective randomization ITT	nominal	Yes / No
data_SAR	No report	date_1arrhythmia_ITT_SAR 	Date of 1st arrhythmia after effective randomization ITT	date	n.a.
data_SAR	descr.	days_effrand_to_1arrhythmia_ ITT_SAR 	Days from effective randomization to 1st arrhythmia or termination ITT	scale	n.a.

### **21.3. Treatment of Missing and Spurious Data**

Spurious data, which were not clarified by the query process before CDMS closure, are indicated. If appropriate, descriptive and inferential analyses are performed both with /without such data.

#### **21.1. Exclusion of Particular Information**

No data from the previous defined analysis set are excluded from the analysis except those defined in chapter 5.5, if applicable.

#### **21.2. Descriptive Analyses**

If applicable, mean and median survival times are presented by using the Kaplan-Meier estimates. Kaplan-Meier survival figures are presented for illustration.

Other descriptive data will be presented via tables as specified in chapter 5.1.

#### **21.3. Hypotheses & Statistical Tests**

Differences of the survival curves BioMonitor versus control group are tested for statistical inference with the log-rank test.

The hazard ratio for the BioMonitor versus control group including 95%CI is calculated with the Cox regression model. In case of doubt about the validity of the Cox model, the assumption of proportional hazards is checked graphically by log-minus-log survival versus log-time plots.

## 22. Other sec. EP: Type of initiated therapies

The main objective of this endpoint is to describe in an explorative fashion which therapies are introduced to patients as consequence of BioMonitor detected arrhythmias. Therefore an internal adjudication board classified the information given in text entries of relevant AE reports with respect to cardiac rhythm, initiated or changed drug therapy, and initiated device therapy.

### 22.1. Analysis set

This endpoint is analyzed exclusively for the final statistical analysis report based on the ITT analysis set.

### 22.2. Variables

*CIP Chapter 8.3.3.10 Type of initiated therapies.*

*Evaluation of the diagnoses and consequent type of therapies based on ICM-detected arrhythmias.*

Data file: Identifier parent_record_id (related to the AE record ID)	Notes	Variable name	Variable label	Variable level	Nominal values
internal_adjudication	descriptive * #	adj_rhythm_multi	Rhythm	nominal	Atrial fibrillation Atrial flutter AV block Bradycardia frequent VPBs non-sustained VT sustained VT polymorphic VT/VF Other SVT Pause None
internal_adjudication	descriptive *	adj_drug	Drug	nominal	Antiarrhythmic BB Diuretic OAC Other None
internal_adjudication	Case listing	adj_drug_txt	Drug text	text	n.a.
internal_adjudication	descriptive #	adj_device	Device	nominal	Ablation Cardioversion ICD Other PM None
internal_adjudication	Case listing	adj_device_txt	Device text	text	n.a.

\*2x3 contingency table; # 2x3 contingency table

 analysis\_set\_itt\_SAR = Yes

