## Further data of interest

To assess in a descriptive manner, the types and number of therapeutic interventions administered after arrhythmias detected by remote monitoring.

Utility values for an economic evaluation will be estimated by using the EQ-5D-5L questionnaire.

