## 1.2. General information

The text contains verbatim excerpts from the CIP Version 1.0. Such excerpts are italicized with grey background.

The main aspects and the design of the clinical investigation are presented in chapters 2, 3, and 4.

General statistical procedures are summarized in chapter 5. Those methods are used in case there is no other instruction within this document.

Definitions of the specific dates, e.g. effective randomization and termination are presented in chapter 0.

The analysis sets are defined in chapter 7.

Data for the CONSORT diagram and baseline data are handled in chapters 8 and 9.

The primary endpoint is handled in chapters 10 and 11, and the secondary endpoints are handled in the following chapters. Thereby the following statistical considerations are specified:

- Definition of the analysis set for the following analyzes, e.g. excluding patients without any measured or imputed data for this endpoint.
- Definition of the endpoint(s) to be analyzed including references to the source data, e.g. CRF sheet and item.
- Treatment of missing and spurious data for evaluation of the above endpoint(s).
- Exclusion of particular information from the evaluation of the above endpoint(s) in addition to the exclusion of patients from the analysis set.
- Statistical alternative hypothesis/hypotheses (HA) to analyze the above endpoint(s).
- Statistical tests intended to analyze the above hypothesis/hypotheses.

In case some variables, which are needed to analyze the pre-specified endpoints, are currently not included in the CDMS, they are indicated with yellow background and the Statistical Analysis Plan (SAP) has to be updated before the first interim analysis or the final analysis.

All variables are defined in tables using the following columns:

Data file	Name of a data file exported from the CDMS with one data row per unique identifier (e.g. patient-specific "patient_display_ID_full" or event-specific "record_ID").  A new data file (e.g. "data_SAR") might be generated by merging all relevant data from the original CDMS data files and generating derived variables (e.g. BMI from weight and height or date of first AE episode).
Notes	Information whether data has to be presented with descriptive methods as defined in the following sub-chapter, data for listings, or data needed for generating of derived variables only.

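### SAP 22.2 holds one drug value and one device value per AE, so a second drug class or a second device therapy cannot enter the therapy tables

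*SAP*

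**What the plan says.** SAP 22 describes which therapies followed arrhythmias found by the BioMonitor. An internal board classified the AE text by rhythm, drug and device. The file in SAP 22.2 is identified as "Data file: Identifier parent_record_id (related to the AE record ID". It has three coded nominal variables:

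- rhythm: "Atrial fibrillation Atrial flutter AV block Bradycardia frequent VPBs non-sustained VT sustained VT polymorphic VT/VF Other SVT Pause None"
- drug (adj_drug): "Antiarrhythmic BB Diuretic OAC Other None"
- device (adj_device): "Ablation Cardioversion ICD Other PM None"

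Two text fields, adj_drug_txt and "adj_device_txt", are reported as case listings. Rhythm is to be crossed with drug and with device, and the footnote gives the sizes as "2x3 contingency table; # 2x3 contingency table".

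SAP 1.2 defines a data file as "Name of a data file exported from the CDMS with one data row per unique identifier". The protocol synopsis, under Further data of interest, undertakes to describe "the types and number of therapeutic interventions administered after arrhythmias detected by remote monitoring". Protocol 8.3.3.10 defines the secondary endpoint more narrowly, as the diagnoses and the type of therapy that followed. SAP 22 plans no statistical test for it.

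**The concern.** One arrhythmia can lead to more than one therapy of the same kind. A patient with newly found atrial fibrillation may start an anticoagulant and a beta-blocker, or have a cardioversion and later an ablation. Protocol 18.1 makes this more likely to fall on one record: a recurrence of an arrhythmia already reported needs no new AE form unless it becomes serious. With one value per field, the coder has to choose, and the SAP gives no rule for choosing.

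This endpoint is the trial's account of what monitoring led to. If the tables hold one drug per AE, the number of therapies is too low, and the share of each class depends on which one was written down. A reader who wants to know how often anticoagulation followed a detected arrhythmia could get too low a figure.

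**Working it through.** **Is the coding single-response?** Four places in the SAP bear on this.

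1. SAP 1.2 sets one row per identifier, and the identifier in SAP 22.2 is parent_record_id.
2. SAP 10 has a file with several lines per event (the votes of the endpoint committee members), but its tables label that file by record_id. They use parent_record_id for the derived file, which has one result per event after the 2-of-3 or chair rule.
3. SAP 22 sends its tables to the templates in SAP 5.1. The template for more than two categories is single-response: the NYHA counts 1 + 3 + 3 + 1 = 8 equal the 8 non-missing patients, and 12.5 + 37.5 + 37.5 + 12.5 = 100%.
4. Where several answers can apply, SAP 9.2 uses separate items: True/False for each MI treatment and each coronary vessel, and Yes/No for each discharge medication (concm01 to concm11).

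Taken together, the plan as written holds one drug value and one device value per AE.

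**Which combinations are affected?** Leaving out None, there are 5 drug classes and 5 device types.

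- One drug with one device: 5 x 5 = 25 pairs, all kept, because the fields are separate.
- Two drug classes: 5 x 4 / 2 = 10 pairs, of which only one member can be coded.
- Two device types: 5 x 4 / 2 = 10 pairs, likewise.

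**How large could the undercount be?** The documents give no frequency of double therapy. Assume that a share p of N drug-treated AEs starts exactly two listed classes and the rest start one. Initiations number N(1 + p), the table counts N, and Np are missed. The uncounted share is p/(1 + p):

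| assumed p | p/(1+p) | uncounted share |
|---|---|---|
| 0.2 | 0.2/1.2 | 17% |
| 0.4 | 0.4/1.4 | 29% |
| 0.6 | 0.6/1.6 | 38% |

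**Table size.** The stated 2x3 means 6 cells. It cannot be reproduced from the listed values:

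| layout | cells |
|---|---|
| rhythm (11) x drug (6) | 66 |
| rhythm (11) x device (6) | 66 |
| the same, with Other and SVT as two rhythm values (12 x 6) | 72 |
| the same, without None (10 x 5) | 50 |
| drug x device (6 x 6) | 36 |
| arm x drug, or arm x device (2 x 6) | 12 |
| arm x rhythm (2 x 11) | 22 |

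None is 2x3, and no rule for collapsing categories is given.

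**The case against.** The strongest reply is that the SAP is silent rather than wrong. Nowhere does it say that a therapy is discarded. The board's form is not shown, single choice is inferred, and the committee data in SAP 10 show that one parent_record_id can gather several lines. The silence is real. But those lines are votes reduced by a stated rule to one result per event, and SAP 22 has no such rule. If several lines per AE were meant, the counting unit and the denominator would be undefined, so the text would still need a change.

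A reader might infer that one therapy is lost whenever an arrhythmia leads to two. The documents do not support that: any drug plus any device is kept. Nor do they show that information is lost from the report, because the case-listed text may name the second therapy. What is affected is the frequency tables.

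It is also fair that the promise of a number of interventions stands under Further data of interest and not in Protocol 8.3.3.10. It concerns the same therapies, however, and no other SAP chapter counts them. SAP 23 takes only the first.

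The 2x3 label alone is clerical, since the categories stand directly above it. Collapsed tables may have been intended.

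**Conclusion.** The point holds for two drug classes, or two device therapies, on one AE: only one can enter the frequency tables. The tables can therefore undercount therapies and understate a class such as oral anticoagulation. This rests on reading SAP 22.2 as single-response, which SAP 1.2, 5.1 and 10 support but SAP 22 does not state outright.

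The size is unknown. The 17% to 38% range follows from assumed values of p and is not an estimate for this trial. A reader might go further and take p itself as the understatement of one class, for example 40 percentage points of drug-treated AEs at p = 0.4. That is a ceiling: it needs the class to be started in every two-drug AE and to be the uncoded one every time. Nothing in the documents suggests this.

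The endpoint is exploratory and has no test, and it feeds neither the primary analysis nor the formally tested secondary hypothesis. This is a cheap improvement, not a threat to the trial's conclusions.

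**What to change.** - Replace adj_drug by one Yes/No variable each for antiarrhythmic, BB, diuretic, OAC and other. Replace adj_device by one each for ablation, cardioversion, ICD, PM and other. Fill them from adj_drug_txt, adj_device_txt and the AE text already classified.
- Report the number of AEs and the number of patients with each class, and the total number of interventions. State whether that total counts classes or also repeats within a class.
- Replace the 2x3 label by rhythm x drug class and rhythm x device class with the listed categories, or state the collapsing rule. Say that an AE may count in more than one column, so percentages need not sum to 100.
- Update the closing sentence of SAP 22, which says that no classification scheme exists yet, although SAP 22.2 lists one.

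The cost is limited re-coding of text the board has already read, plus new table shells. No new data are needed. The downside is some repeated work for a descriptive endpoint.

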### **22.3. Treatment of Missing and Spurious Data**

Spurious data, which were not clarified by the query process before CDMS closure, are indicated. If appropriate, descriptive and inferential analyses are performed both with /without such data.

#### **22.1. Exclusion of Particular Information**

No data from the previous defined analysis set are excluded from the analysis except those defined in chapter 5.5, if applicable.

#### **22.2. Descriptive Analyses**

Descriptive data are presented via tables as specified in chapter 5.1.

#### **22.3. Hypotheses & Statistical Tests**

A broad range of diagnoses and therapies can be expected for the study population. A reasonable pre-defined scheme to classify the events has not yet been developed. Thus, there are no pre-specified statistical tests for this endpoint.

## 23. Other sec. EP: Time to 1st therapy.

### 23.1. Analysis set

This endpoint is analyzed exclusively for the final statistical analysis report based on the ITT analysis set.

### 23.2. Variables

#### CIP Chapter 8.3.3.11 Time to 1st therapy

*Assessment of the time from randomization to first therapy. In this context therapy is the attempted remediation of the patient's regular heartbeat. To ensure a standardized proceeding, guideline-based therapy recommendations will be provided to the participating investigators within a separate manual.*

This endpoint comprises therapies reported in AE report CRF, irrespective of the cause of the patient being in the investigational site. The patient may be called in by an investigator after arrhythmias were detected in the BM or after a physician outside the investigational site assumed it appropriate to send the patient to a highly competent cardiological site. Changes of therapy prescribed by a general practitioner or another physician outside the investigational site are not considered.

Since the investigational sites are highly specialized cardiological units, it is not assumed that they will prescribe a relevant amount of non-cardiovascular therapies. All cardiovascular therapies will be considered for this endpoint, also if they are not directly relevant for the regular heartbeat as stated in the CIP. Especially, this also includes therapies directed at diuresis, blood pressure, coagulation status or ischemia, since all these treatments do also interact with the heart rhythm in some way.

Data file: Identifier record_id	Notes	Variable name	Variable label	Variable level	Nominal values
general_notification	No report	visit_date	Date of patient visit in investigational site	date	n.a.
general_notification_ data_SAR	No report	therapy_general_date	Date of the guideline-recommended change of therapy after an AE	date	n.a.

Data file: Identifier record_id	Notes	Variable name	Variable label	Variable level	Nominal values
arrhythmia_notification	No report	visit_date	Date of patient visit in investigational site	date	n.a.
arrhythmia_notification_ data_SAR	No report	therapy_arr_date	Date of the guideline-recommended change of therapy after an AE	date	n.a.

Data file: Identifier record_id	Notes	Variable name	Variable label	Variable level	Nominal values
adverse_events	No report	parent_record_id	NEW: Record ID of the parent document, i.e. the general notification CRF or arrhythmia notification CRF related to the AE CRF	nominal	...
adverse_events	No report	arrchange_yn	Does the arrhythmia require guideline- recommended change of therapy	nominal	Yes / No

 analysis\_set\_itt\_SAR = Yes

Data file: Identifier patient_display_id_full	Notes	Variable name	Variable label	Variable level	Nominal values
data_SAR	No report	any_therapy_ITT_SAR 	Any therapy after effective randomization (attempted remediation of the patient's regular heartbeat) ITT	nominal	Yes / No
data_SAR	No report	date_1therapy_ITT_SAR 	Date of 1st therapy (attempted remediation of the patient's regular heartbeat) ITT	date	n.a.
data_SAR	descr.	days_effrand_to_1therapy_ITT_SAR 	Days from randomization to 1st therapy (attempted remediation of the patient's regular heartbeat) or termination ITT	scale	n.a.

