### 8.4.1 CRF and Forms

All parameters and measurements that are recorded within the study are described in this section and are documented on the following eCRFs and forms. Table 2 provides an overview of eCRFs and procedures.

Data collected during study initiation and termination

- Enrollment CRF
- Baseline CRF
- Implantation CRF
- Discharge CRF
- Termination visit CRF
- Study termination CRF
- Elective Replacement Indicator (ERI) form
- Remote Assistant form
- Protocol deviation / Protocol non-compliance CRF

Data collected due to adverse events (AE)

- Adverse event CRF
- Concomitant medication log eCRF, required only if AE is suspected to be due to a medication
- Device deficiency (DD) CRF

Data collected by the CRO performing the telephone follow-up

- Telephone follow-up questionnaire (see section 9.6)
- Quality of life questionnaires (see section 9.6)

Data resulting from Home Monitoring messages and other medical events requiring tertiary level care

- Arrhythmia notification form (see section 9.5)
- General notification form (see section 9.5)
- IHF event notification form (see section 9.5)

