**Table 2: Overview CRFs and Investigations**

Investigation	Enrollment	Baseline	Implantation	Discharge	Telephone contacts (every 6 months)	Arrhythmia notification form	General notification form	IHF notification form	Termination
Patient informed consent	x								
Verification of in- and exclusion criteria	x								
Patient demographics		x							
NYHA class		x							x
Echo parameters		x							
Specification of MI	x								
Medical history/Co-morbidities		x							
Cardiovascular medication				x					x
Lab parameters				x					
Randomization result		x							
BioMonitor implantation			x						
BioMonitor interrogation			x						
BioMonitor programming			x						
Adverse events		x	x	x	x	x	x	x	x
Arrhythmia classification						x			
Evaluation of necessity to contact patient						x	x	x	
Patient interview						x	x	x	x
Evaluation of necessity of diagnostic procedure						x	x	x	
Telephone follow-up questionnaire					x				
Quality of life questionnaires					x				
Documentation of: - reason for visit - performed examinations, therapies, modifications						x	x	x	
Documentation of: - regular or premature termination - reason for premature termination									x

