**Table 2: Overview CRFs and Investigations**

Investigation	Enrollment	Baseline	Implantation	Discharge	Telephone contacts (every 6 months)	Arrhythmia notification form	General notification form	IHF notification form	Termination
Patient informed consent	x								
Verification of in- and exclusion criteria	x								
Patient demographics		x							
NYHA class		x							
Echo parameters		x							
Specification of MI	x								
Medical history/Co-morbidities		x							
Cardiovascular medication				x					
Lab parameters				x					
Randomization result		x							
BioMonitor implantation			x						
BioMonitor interrogation			x						
BioMonitor programming			x						
Adverse events		x	x	x	x	x	x	x	x
Arrhythmia classification						x			
Evaluation of necessity to contact patient						x	x	x	
Patient interview						x	x	x	
Evaluation of necessity of diagnostic procedure						x	x	x	
Telephone follow-up questionnaire					x				
Quality of life questionnaires					x				
Documentation of: - reason for visit - performed examinations, therapies, modifications						x	x	x	
Documentation of: - regular or premature termination - reason for premature termination									x

*CIP chapter 9.1 Overview*

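### SAP 23.2 lists no date source for site therapies recorded only on the IHF event notification form, so time to first therapy may miss them or date them late

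*SAP*

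**What the plan says.** SAP 23.2 first sets the scope: "This endpoint comprises therapies reported in AE report CRF, irrespective of the cause of the patient being in the investigational site". It then removes one group on purpose: "Changes of therapy prescribed by a general practitioner or another physician outside the investigational site are not considered".

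The variable tables that follow offer a visit date from two data files only, general_notification and arrhythmia_notification, each paired with its own therapy date. An adverse event is tied to one of them through parent_record_id, labelled "NEW: Record ID of the parent document, i.e. the general notification CRF or arrhythmia notification CRF related to the AE CRF". The time variable is "Days from randomization to 1st therapy (attempted remediation of the patient's regular heartbeat) or termination ITT", so a patient with no therapy date runs to termination. SAP 23.3 then specifies a log-rank test and a Cox hazard ratio with 95% CI.

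The protocol has three notification forms. Section 8.4.1 lists the arrhythmia, general and IHF event notification forms together, and Table 2 ticks the row "Documentation of: - reason for visit - performed examinations, therapies, modifications" under all three. SAP chapter 4 reprints the table with the same three ticks.

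**The concern.** The declared scope and the declared sources do not match. The scope is every site therapy in an adverse event report, whatever the reason for the visit. The sources are two of the three forms on which such a visit can be recorded. Two patients with the same treatment on the same day could therefore be handled differently because of the form used.

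The mismatch need not be neutral between arms. Under protocol 9.5 the arrhythmia form is started by the central ECG board from Home Monitoring data, so only BioMonitor patients can have one, and the visit date on it is a listed source. Control patients have one covered form out of two; BioMonitor patients have two out of three. If the control arm loses a larger share of its therapies, BioMonitor patients appear to be treated sooner than they were relative to control. SAP 1.1 makes the inferential analyses of the endpoints mandatory in the final report, so the result will be shown.

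**Working it through.** **Planning figure.** There is none to reproduce for this endpoint. The 372 events and hazard ratio of 0.7452 in protocol 11.2 concern MACE and play no part here.

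**Sources side by side.**

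| Form | Table 2 row on visits and therapies | Date source in SAP 23.2 | Arms that can have it |
|---|---|---|---|
| Arrhythmia notification | ticked | yes | BioMonitor only |
| General notification | ticked | yes | both |
| IHF event notification | ticked | none listed | no restriction stated |

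SAP 1.2 says that all variables are defined in tables. No IHF data file or date variable appears in chapter 23, nor in the form lists of SAP 5.5 and 6.6. So, on the listed variables, an adverse event whose parent is an IHF form yields no therapy date. If the patient later has a therapy on a listed form, the event is dated late; if not, the patient is censored at termination.

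**Effect on the hazard ratio.** Let qC and qB be the shares of site therapies recorded only on the IHF form in control and BioMonitor. If therapies arise at a constant rate and each is recorded independently, dropping a share q multiplies the hazard of the first recorded therapy by (1 − q). This already allows for late dating. Then

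observed HR = true HR × (1 − qB) / (1 − qC).

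The documents give no value for qC or qB, so every share below is an assumption. The true HR is 1. The last two columns give the chance of two-sided p < 0.05 by the normal approximation: with θ = √(d/4) × ln(HR), it is Φ(θ − 1.96) + Φ(−θ − 1.96) for d recorded therapies.

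| qC / qB | Observed HR | d = 200 | d = 400 |
|---|---|---|---|
| equal, any level | 1.00 | 5% | 5% |
| 10% / 5% | 0.95/0.90 = 1.06 | 7% | 8% |
| 20% / 10% | 0.90/0.80 = 1.13 | 13% | 22% |
| 40% / 20% | 0.80/0.60 = 1.33 | 53% | 82% |
| 10% / 20% | 0.80/0.90 = 0.89 | – | – |

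**Whether the loss would be larger in control.** Let a be the share of BioMonitor therapies on the arrhythmia form and g the control share on the IHF form, so qC = g. Two assumptions give different answers.

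- *The arrhythmia form displaces general and IHF forms in proportion.* Then qB = g(1 − a), and HR = (a + (1 − a)(1 − g))/(1 − g). For (a, g) = (0.3, 0.2), (0.5, 0.3) and (0.7, 0.4) this gives 0.86/0.80 = 1.08, 0.85/0.70 = 1.21 and 0.88/0.60 = 1.47.
- *It displaces general forms first.* Then qB is the smaller of g and 1 − a. The same pairs give qB = 0.2, 0.3 and 0.3, and HR = 0.80/0.80 = 1.00, 0.70/0.70 = 1.00 and 0.70/0.60 = 1.17.

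With g = 0 there is no bias under either assumption.

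**The case against.** The strongest reply is that the two listed forms already match the routes by which patients reach the site. Protocol 9.5 assigns detection-triggered visits to the arrhythmia form, and referred or self-presenting patients to the general form. SAP 23.2 describes the same routes: called in after a detection, or sent by an outside physician. Protocol 8.4.1 points to section 9.5 for the IHF form, but that section does not describe it. The telephone provider tells sites about events learned by phone, and these can include care given elsewhere, which the SAP excludes on purpose. The share of in-scope therapies found only on the IHF form could be close to zero.

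That stands as a limit on size. It does not remove the mismatch. Table 2 gives the IHF form the same ticks as the general form for patient contact, interview, diagnostic procedures, and visit and therapy. Protocol 8.4.1 places it among forms for events needing tertiary care, which protocol 9.4 links to the investigational site. Outside care on the form calls for a filter, not for leaving the form out.

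A second reply is that the text of footnotes 121 to 123, attached to the derived therapy variables, was not available for this check. That also stands: the handling is inferred from the listed variables. A footnote that closed the gap would, however, need a variable that the tables do not declare.

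A reader might go further and infer that these therapies are censored, mostly in control, so that the result is biased toward BioMonitor. The documents do not support that. They give no counts by form or arm; protocol 8.2.3 keeps telephone calls equally frequent in both arms; and a later therapy on a listed form gives a late event, not censoring.

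**Conclusion.** The conflict between scope and listed sources is real: SAP 23.2 claims all site therapies in adverse event reports but lists no date for those recorded only on the IHF form. Such therapies are missed or dated late, unless the unseen footnotes say otherwise.

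A larger proportional loss in control is plausible, because only BioMonitor patients have the arrhythmia form, and it would push the hazard ratio above 1. Neither direction nor size is established. Under the assumed shares and no true difference, the ratio runs from 0.89 to 1.47, and it is exactly 1.00 when losses are equal or absent.

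The reach is narrow. Protocol 7.3 pre-defines no hypothesis for the other secondary objectives, and the pass criterion in protocol 11.5 does not involve this endpoint. Only its own log-rank test and hazard ratio are affected. The point merits correction because the conflict is within the plan's own text and the form is already part of data collection.

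**What to change.** In SAP 23.2:

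1. Add the IHF event notification form as a third parent and date source, using the visit date documented on it. Restrict it to therapies given at the investigational site, so that the exclusion of outside physicians is kept.
2. Define the first therapy as the earliest date over the three forms, in both arms.
3. Report therapy counts by source form and arm, so that readers can see whether the IHF form matters.

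Do not fall back generally on a date from the adverse event record when no notification form is linked. The adverse event dates listed elsewhere in the SAP (onset, seriousness, end, hospitalization, arrhythmia documentation) are not therapy dates, and the fallback could admit outside treatment. If used at all, it belongs in a sensitivity analysis limited to confirmed site therapies.

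The cost is a short SAP edit and a small change to the derivation. The SAP names no IHF data file or variable, so the visit-date field has to be confirmed in the database first. If the form turns out to hold no site therapies, a sentence saying so is enough.
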